# 12.1.1 Extracutaneous Response Criteria

Response criteria will be based on assessment following 2 cycles and subsequent assessments will be made every 3 cycles thereafter (e.g. after cycle 5, 8, 11 etc). The criteria are as follows (GTD = Greatest Transverse Diameter; SPD = Sum of the Products of the Greatest Diameter):

# Complete Remission (CR):

- No clinical, radiographic or diagnostic evidence of disease.
- No disease related symptoms.
- Abnormal biochemical values (e.g., LDH) clearly attributable to lymphoma must have normalized.
- Lymph nodes, nodal masses regressed to "normal" size:
- If > 1.5 cm before treatment regressed to  $\leq$  1.5 cm in GTD.
- If 1.1 to 1.5 cm before treatment, regressed to ≤ 1 cm in GTD (or >75% in SPD).
- Spleen and all previously enlarged organs decreased in size. Spleen must not be palpable on exam
- Bone marrow free of disease on repeat aspirate and biopsy if initially positive.
- Normalization of PET scan.

# Complete Remission/unconfirmed (CRU):

Patients meeting the above criteria for CR with the following exceptions:

- Residual node mass of >1.5 cm in GTD regressed by > 75% in SPD.
- Individual nodes previously confluent regressed by >75% in SPD
- Indeterminate bone marrow (increased number or size of lymphoid aggregates without cytologic or architectural atypia).

## Partial Remission (PR):

- Greater than or equal to 50% decrease in SPD of the six largest dominant nodes/nodal masses.
- No increase in size of other nodes, liver or spleen.
- Splenic and hepatic nodes regressed at least 50% in SPD.
- No new sites of disease.
- Bone marrow and organs other than the spleen and liver cannot be considered for evaluation for PR because involvement at these sites is considered evaluable but not measurable.

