# 6.1 CRITERIA FOR SUBJECT ELIGIBILITY

# 6.2 Subject Inclusion Criteria

- a) Pathologically confirmed B- or T-cell lymphomas at the enrolling institution, including stage ≥ lb CTCL, which has relapsed or progressed after at least one systemic therapy.
  - Hodgkin lymphoma is allowed and will be classified as a B-cell lymphoma in the phase IIA portion.
- b) Age ≥ 18,
- c) Previous systemic anti-cancer therapy must have been discontinued at least 3 weeks prior to treatment and adverse effects must have resolved to ≤Grade 1 or baseline. In the phase Ila portion, in progressing subjects a 2 week washout may be allowed after discussion with the MSK Principal Investigator.
- d) Previous radiation, hormonal therapy, and/or surgery must have been discontinued or completed at least 2 weeks prior to treatment in this study and adverse effects must have resolved. Lymph node or other diagnostic biopsies within 2 weeks are not considered exclusionary.
- e) ECOG≤2
- f) Meet the following laboratory criteria:
  - Absolute neutrophil count ≥ 1.0/mm³,
  - Platelet count ≥ 80 K/μ (in the Phase IIa portion, if thrombocytopenia is due to bone marrow involvement platelet count must be ≥ 50 K/μL),
  - Phase Ib subjects must have calculated creatinine clearance ≥ 50ml/min by Cockcroft-Gault formula, phase IIa subjects must have calculated creatinine clearance ≥ 40ml4/min by Cockcroft-Gault formula.
  - Total bilirubin ≤ 1.5 x upper limit of normal (ULN). AST (SGOT) and ALT (SGPT) ≤ 3 x ULN.
- g) Measurable disease for phase IIa portion only.
  - Lymphoma (includes CTCL patients who are without evidence of the disease in the skin): CT or PET/CT by modified Cheson criteria with incorporation of PET.
  - CTCL: mSWAT >0, or absolute Sezary count ≥ 1000 cells/μL.

- h) All study participants must be registered into the mandatory Revlimid REMS® program, and be willing and able to comply with the requirements of the REMS® program.
- i) Short course systemic corticosteroids for disease control, improvement of performance status or non-cancer indication (≤ 7 days) must have been discontinued at least 6 days prior to study treatment. Stable ongoing corticosteroid use (≥ 30 days) up to an equivalent dose of 15 mg of prednisone is permissible.
  - Topical steroids that have been used for > 3 weeks may be continued (CTCL only).

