# 12.1 CRITERIA FOR THERAPEUTIC RESPONSE/OUTCOME ASSESSMENT

Response and progression of disease will be evaluated in this study using a modification of the international criteria proposed by the modified Cheson criteria with incorporation of PET/CT. [Cheson B, 2007]. The imaging modality for evaluation will be dependent on disease subtype. For aggressive lymphomas (e.g. DLBCL, PTCL, HL), PET/CT will be used for evaluation of response. For indolent lymphomas, CT alone or PET/CT may be used at the discretion of the treating physician. For CTCL, please see Section 12.0.2.

Measurable disease: Measurable lesions are defined as those that can be accurately measured in at least one dimension (longest diameter to be recorded) as  $\geq$  15 mm with conventional techniques (PET, CT, MRI, x-ray). All tumor measurements must be recorded in millimeters (or decimal fractions of centimeters).

Non-measurable disease: All other lesions (or sites of disease), including small lesions (longest diameter < 15 mm), are considered non-measurable disease. Bone lesions, leptomeningeal disease, ascites, pleural/pericardial effusions, lymphoma

Memorial Sloan Kettering Cancer Center IRB Number: 14-179 A(6)
Approval date: 12-Dec-2017

Administrative Update 1 : 06-Dec-2018

cutis/pulmonis, inflammatory breast disease, abdominal masses (not followed by CT or MRI), and cystic lesions are all non-measurable.

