# **Progressive Disease (PD):**

- In patients previously CR, CRUCRU, PR or SD.
- Greater than or equal to 50% increase in SPD of any previously identified abnormal node.
- Appearance of any new lesion during or at the end of therapy

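### An extranodal mass outside spleen and liver can qualify a patient for phase IIa as measurable disease, but the written criteria score neither its shrinkage as PR nor its growth as PD

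*Combined protocol and SAP*

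**What the plan says.** Inclusion criterion g (Section 6.2) asks for "Measurable disease for phase IIa portion only", assessed for lymphoma by "CT or PET/CT by modified Cheson criteria with incorporation of PET". It does not restrict the site of disease.

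Section 12.1 supplies the definition: "Measurable lesions are defined as those that can be accurately measured in at least one dimension", with a threshold of 15 mm on PET, CT, MRI or x-ray. It goes on to list the non-measurable sites: small lesions, bone, leptomeningeal disease, effusions, and a closing group that reads "cutis/pulmonis, inflammatory breast disease, abdominal masses (not followed by CT or MRI), and cystic lesions are all non-measurable". An abdominal mass that is followed by CT or MRI is therefore not on the list.

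Section 12.1.1 gives the response rules:

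- **PR** is "Greater than or equal to 50% decrease in SPD of the six largest dominant nodes/nodal masses", with no increase in other nodes, liver or spleen, a spleen and liver regression clause, and no new disease sites. The last bullet reads "Bone marrow and organs other than the spleen and liver cannot be considered for evaluation for PR", on the ground that disease there can be evaluated but not measured.
- **PD** is "Greater than or equal to 50% increase in SPD of any previously identified abnormal node", or any new lesion.
- **SD** is whatever falls short of PR without meeting PD.

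Section 4.2 defines ORR as a best response of CR/CRu or PR. It ends EFS at documented progression, change in therapy or death, and DOR likewise ends at progression, change of therapy or death.

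**The concern.** The protocol uses two notions of measurability. At entry it is a matter of size, with a list of excepted sites. In the PR rule it is a matter of anatomy, and every organ except spleen and liver is ruled out. For an organ mass of 15 mm or more that is followed by CT and is not on the excepted list, both statements cannot be true.

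The practical result is that a lesion can bring a patient into the efficacy set and then have no rule by which a partial change in it is scored. The resulting errors run in known directions. Partial shrinkage that goes uncounted lowers ORR. Growth that goes uncounted lengthens EFS and, in a patient already in response through nodal disease, DOR. Progression is also a reason to stop treatment (Sections 4.3 and 13.2 and the phase Ib treatment plan in Section 9.3), so the gap is not confined to the summary tables.

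**Working it through.** The plan states no figure on this point, so there is nothing to reproduce. The check sets the rules side by side and applies them to cases.

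**1. Entry.** Take a patient whose only disease is a 40 x 40 mm bowel mass followed by CT. It exceeds 15 mm, and it is an abdominal mass followed by CT, so it is not on the non-measurable list. Under Sections 6.2 and 12.1 it is measurable disease.

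**2. Shrinkage to 20 x 20 mm.** The product of diameters goes from 40 x 40 = 1600 mm² to 20 x 20 = 400 mm², and 400/1600 - 1 = -75%. The PR size rule counts nodes and nodal masses, and the last PR bullet bars the bowel. PR is not met. CR is not met, because disease remains. Result: SD. A soft-tissue mass fails on the size rule alone, since the exclusion bullet names marrow and organs only.

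**3. Growth to 60 x 60 mm.** 60 x 60 = 3600 mm², and 3600/1600 - 1 = +125%. The growth limb of PD requires a node. Without a new lesion, PD is not met. Result: SD.

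**4. A patient with nodal disease as well.** The nodes shrink by at least 50% while the known bowel mass grows as in step 3. The no-increase condition names other nodes, liver and spleen, but not other organs. PR stands and PD is not met. If liver or spleen disease grows instead, the no-increase condition blocks PR, but the growth is still not PD, because the PD rule refers to a node.

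**5. What stays reachable.** CR remains possible, as does PD by a new lesion at any site, and EFS can end at change of therapy or death. CTCL skin disease has its own PR and PD rules through mSWAT (Appendix D) and is not affected.

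**6. Size for ORR.** Phase IIa has 20 patients, 10 per disease cohort. One responder scored as SD costs 1/20 = 5 points overall or 1/10 = 10 points in a cohort.

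The documents give no share of patients with extranodal-only measurable disease. For illustration, assume *k* of 20 such patients and borrow the response figures that Section 3.5 reports for the two-drug study: ORR 7/13 = 53.8%, PR 5/13 = 38.5%. If the true PR rate is the same in these patients and none of their PRs can be scored:

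expected ORR = 7/13 - (*k*/20) x 5/13

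| *k* of 20 | PRs lost, *k* x 5/13 | Expected ORR | Loss (points) |
|---|---|---|---|
| 0 | 0 | 53.8% | 0 |
| 1 | 0.4 | 51.9% | 1.9 |
| 4 | 1.5 | 46.2% | 7.7 |
| 6 | 2.3 | 42.3% | 11.5 |

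For scale, the normal-approximation 95% half-width at n = 20 is 1.96 x √(0.538 x 0.462 / 20) = 0.22, or about 22 points.

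**7. Size for EFS.** After cycle 2, assessments come every three 21-day cycles. If growth seen at one scheduled scan is counted only at the next, because a new lesion has appeared by then, recorded EFS is longer by 3 x 21 = 63 days, assuming no cycle delays.

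**The case against.** The strongest reply is that the last PR bullet itself settles measurability. If organ disease outside spleen and liver is not measurable, the bowel-only patient fails criterion g and is never enrolled in phase IIa. That reading is possible, but it contradicts Section 12.1, which treats a CT-followed abdominal mass as measurable. It would move the problem from response to eligibility without removing it, and it does nothing for the patient in step 4, who enters on nodal disease.

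A second reply is that the cited modified Cheson criteria fill the gap. The protocol says that it uses a modification of them and then writes out the criteria to be applied. That written list has no rule for partial change in an extranodal mass. The PET-negative PR category requires PR to be met first. The response review committee in Section 16.1.2 confirms responses but is given no other rule. On one point the text is arguable: the PR section speaks of splenic and hepatic nodes, so the PD rule might be stretched to discrete deposits in those organs. It would still not reach organ enlargement or masses elsewhere.

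Several limits stand. A reader might infer that any patient with an extranodal mass can neither respond nor progress. The documents do not support that: patients with nodal disease can reach PR or PD through their nodes, and many extranodal sites are listed as non-measurable. A reader might also infer that the two disease cohorts cannot be compared. No comparison between them is planned; Section 14.0 pools them and adds descriptive subset analyses. Inflated DOR is mainly an issue for nodal responders with isolated extranodal growth, because an extranodal-only patient has no DOR unless CR is reached. Clear clinical growth may also lead to a change of therapy, which ends EFS, though perhaps later than the growth itself.

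**Conclusion.** The point holds within those limits. Sections 6.2, 12.1 and 12.1.1 contradict each other on what is measurable. As written, a large change in an eligible extranodal mass outside spleen and liver scores as SD in either direction, unless it amounts to CR or comes with a new lesion. In a nodal responder, growth of such a mass neither removes the PR nor counts as PD.

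The effect is 5 ORR points per missed responder in 20 patients, or 10 in a cohort of 10. The total depends on a share of patients that the documents do not state. Under the illustrative assumptions above, the expected loss is about 2 to 12 points for 1 to 6 such patients. That is smaller than the sampling half-width of about 22 points, but it is systematic.

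A reader might take this as a defect that threatens the trial's main conclusion. The documents do not support that. The primary endpoint is MTD and safety (Section 2.1). Efficacy is secondary and descriptive, with no target rate or test, and the DLT-based stopping rule in Section 14.0 does not use response. This should be fixed, but it is not a must-fix item. The conclusion rests on reading the Section 12.1.1 list as the operative criteria.

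**What to change.** Make one definition of measurable lesion govern entry, response and progression. For the response endpoint there are two coherent routes:

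- **Count the masses.** Let the SPD for PR include measurable extranodal masses, and limit the last PR bullet to bone marrow and the sites that Section 12.1 lists as non-measurable. SPD needs two diameters, whereas Section 12.1 asks for only one measurable dimension, so state that a lesion counted in SPD must be measurable in two.
- **Exclude the masses.** State in Section 12.1 and criterion g that extranodal masses outside spleen and liver do not qualify as measurable disease. This settles entry and PR, but leaves open how growth of such a mass is scored in a patient enrolled on nodal disease.

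Progression also ends treatment, so the sponsor must reconcile the PD wording in Section 12.1.1 with Section 12.1. No clinical rule is proposed here.

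The cost is protocol wording and the tumour-measurement eCRF page, with no added scans or patients. Some scans already assessed may need to be re-read and some responses or progressions reclassified. Any reclassification should be documented and reported.

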#### PET negative Partial Remission (PET-PR):

 Patient meets above criteria for PR with resolution of previous PET positive lesions.

# Stable Disease (SD):

 Patients who have achieved less than a partial remission but who have not developed findings consistent with progressive disease.

# **Progressive Disease (PD):**

- In patients previously CR, CRUCRU, PR or SD.
- Greater than or equal to 50% increase in SPD of any previously identified abnormal node.
- Appearance of any new lesion during or at the end of therapy

# 12.1.2 Cutaneous T-cell Lymphoma (CTCL) Response Criteria

Dermatologic responses will be determined by the modified Severity-Weighted Assessment Tool (mSWAT), a standardized approach to measuring the extent and severity of overall skin disease in patients with CTCL. It will be briefly described and full details are provided in Appendix D. The purpose of this description is to optimize intra-observer objectivity and to minimize the potential for intra-observer and inter-observer variability in the measurement of overall skin disease. Only physicians who received training will be permitted to conduct mSWAT assessments during the clinical study. It is essential that physicians adhere as closely as possible to the prescribed procedures so as to reduce measurement error and variability. All efficacy assessments should be performed by the same physician for each patient whenever possible. Physicians will be instructed not to examine previous mSWAT assessments and full body photographs prior to conducting the current mSWAT assessment.

#### 13.1 CRITERIA FOR REMOVAL FROM STUDY

## 13.2 Discontinuation of Study Treatment

Treatment will continue until the occurrence of any of the following events.

- Disease progression
- Institution of alternate therapy or planned stem cell transplantation.
- Adverse event(s) that, in the judgment of the Investigator, may cause severe or permanent harm or which rule out continuation of the treatment regimen.
- Discontinuation of lenalidomide, carfilzomib or romidepsin for any reason.
- Major violation of the study protocol.
- Withdrawal of consent
- Lost to follow up
- Death
- Pregnancy or a positive pregnancy test

#### 14.0 BIOSTATISTICS

The standard dose-escalation scheme for this study is as follows. Patients will be accrued to the study in cohorts of 3. For any given dose an initial cohort of 3 patients will be treated at that dose. The dose level will be escalated if none of the 3 patients exhibits any DLT in the first cycle as defined above. If a DLT is observed in one patient, an additional cohort of 3 patients will be treated at that dose. The dose will be escalated if none of the additional 3 patients exhibits any DLT. Dose-escalation stops and the previous dose will be considered the MTD if 2 or more patients have a DLT. If the previous dose level has been administered to only 3 patients, an additional 3 patients will be enrolled to confirm the result. For this design the probability of escalation is as follows:

True toxicity rate	5%	10%	15%	20%	25%	30%	40%	50%
Probability of escalation	0.97	0.91	0.81	0.71	0.60	0.49	0.31	0.17

Dose escalation will start with dose level 1. A dose level -1 is also added to the design to ensure a minimum level of toxicity (we expect this dose level will be quite tolerable for patients based on the phase I data of romidepsin and lenalidomide). The maximum number of patients needed for this dose escalation design is 30. We estimate accrual to be 2 patients per month. Patients with measurable disease treated at MTD in the phase Ib will be analyzed in phase Ila to further characterize the toxicity of carfilzomib, romidepsin and lenalidomide in combination at the MTD determined by phase Ib. In phase IIa, we plan to enroll patients so that the total number of patients enrolled in each disease type cohort (B-cell lymphoma and T-cell lymphoma) will include 10 patients at the MTD. We estimate accrual to be 1 patient per month in each disease type cohort. To consecutively monitor the safety primary endpoint in the phase IIa portion, we will employ a sequential probability stopping rule for the predefined DLT in the phase lb portion of cycles 1-4. This stopping rule specifies that the study will be terminated if DLT occur in: ≥3/first 6; ≥6/first 12; or if more than 10 patients when the last (20th) evaluable patient has completed the trial have any DLT. This rule has the following stopping probability:

True toxicity rate	5%	10%	15%	20%	25%	30%	35%	40%	50%
Stopping prob.	0.002	0.016	0.049	0.104	0.184	0.289	0.413	0.548	0.797
C									

e

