#### 4.1 OVERVIEW OF STUDY DESIGN/INTERVENTION

# 4.2 Design

We plan to perform an open label phase Ib/IIa study of patients with relapsed/refractory B- and T-cell lymphomas who are treated with carfilzomib, lenalidomide and romidepsin in a 3+3 design (see section 9.2). The phase IIa portion of the study will involve a dose expansion at the MTD to better characterize the efficacy and to inform further disease specific studies.

**Phase Ib**: The phase Ib portion of the study is designed to determine the MTD of carfilzomib, romidepsin and lenalidomide. All patients must have a relapsed or refractory B-cell or T-cell lymphoma. The design is a standard 3+3 dose escalation (**Table 3**) of carfilzomib, romidepsin and lenalidomide. The first cohort will enter at dose level 1. For details please see section 9.2.

Three patients will be initially treated in each cohort until the MTD is determined. If dose level 4 is achieved without DLT after 1 cycle that dose level will be deemed the optimal dose and the study will proceed to a phase lla expansion cohort. Patients treated at MTD in the phase lb portion will be counted towards the phase lla accrual by disease subtype and also for all efficacy and toxicity endpoints unless they did not have measurable disease at point of study entry as allowed in the phase lb portion.

Phase IIa: The phase IIa portion will further assess the toxicity and safety and allow a preliminary assessment of the efficacy of the combination to provide background for a potential future subtype specific phase II study. The assessment of efficacy will be descriptive. At the time of enrollment the patients will be identified as representing two cohorts based upon disease subtype: 1) B-cell lymphoma 2) T-cell lymphoma. Each cohort will enroll 10 patients including those treated at the MTD of the phase Ib portion. The assessment of toxicity and efficacy will be performed within the entire cohort evaluable at MTD. A preplanned exploratory analysis of the toxicity and efficacy of the disease specific cohorts will also be performed. Efficacy measures which will be determined include ORR, TTR, DOR,

Memorial Sloan Kettering Cancer Center IRB Number: 14-179 A(6)
Approval date: 12-Dec-2017

Administrative Update 1:06-Dec-2018

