#### Treatment Plan: carfilzomib/romidepsin/lenalidomide Phase Ila

The phase IIa portion is planned to include 20 patients. Each disease cohort, B-and T-cell lymphoma, will have 10 patients. Patients treated at MTD in the phase Ib cohort (if measurable disease at enrollment) will be included towards the 20 patient total in the phase IIa. The MTD has been determined to be dose level 1; 8 mg/m² romidepsin on days 1 and 8, 15 mg lenalidomide from days 1 - 14, and 36 mg/m² carfilzomib on days 1 and 8. The phase IIa cohort will be evaluated both collectively and by disease subtype.

Patients that have received long-term therapy (greater than one year) with response will be allowed to have their schedule modified to allow less frequent dosing per investigator and primary investigator discretion.

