#### 9.5 **Dose Continuation, Modification and Interruption**

Subjects will be evaluated for AEs at each visit with the NCI CTCAE v4.0 used as a guide for the grading of severity. DLTs as defined will be tabulated in cycle 1 of phase Ib and cycles 1-4 of the phase Ila portion of the study. The toxicity decision rule for the Ila portion is described in Section 14.0. The sections below describe dose reduction steps, instructions for initiation of a new cycle of therapy and dose modifications during a cycle of therapy. Of note, if patient's experiences a greater than 10% change in body weight, dose of romidepsin should be adjusted accordingly. Doses do not need to be adjusted for less than 10% changes in body weight.

# 9.5.1 Instructions for Dose Modifications or Interruption During Phase 1 Cycle 1

There will be no dose reductions in cycle 1 phase 1. Inability to meet treatment criteria will result in holding the dose.

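### The phase IIa stopping-probability table matches a final cut of 10 or more of 20 where the text says more than 10, and it ignores that screened phase Ib patients count among the 20

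*Combined protocol and SAP*

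**What the plan says.** Section 14.0 sets the phase IIa safety rule. The study ends if DLTs, counted over cycles 1-4, occur in "≥3/first 6; ≥6/first 12; or if more than 10 patients when the last (20th) evaluable patient has completed the trial have any DLT". The table beneath is presented as the stopping probability of this rule: 0.002, 0.016, 0.049, 0.104, 0.184, 0.289, 0.413, 0.548 and 0.797 at true DLT rates of 5, 10, 15, 20, 25, 30, 35, 40 and 50%.

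The 20 are not all new patients. In the phase IIa treatment plan (Section 9.3), phase Ib patients treated at the MTD with measurable disease "will be included towards the 20 patient total in the phase IIa". Section 4.2 counts them towards "accrual by disease subtype and also for all efficacy and toxicity endpoints". The same treatment plan reports that phase Ib has finished: "The MTD has been determined to be dose level 1".

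On how the MTD is reached, Section 14.0 stops escalation at 2 or more DLTs and takes the previous dose as the MTD. It adds: "If the previous dose level has been administered to only 3 patients, an additional 3 patients will be enrolled to confirm the result". Section 9.5 gives the counting windows: "DLTs as defined will be tabulated in cycle 1 of phase Ib and cycles 1-4 of the phase" IIa portion.

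**The concern.** Two things separate the table from the rule it is meant to describe.

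**Final cut.** With exactly 10 DLTs in 20 patients, the text lets the study stand and the rule behind the table stops it.

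**Population.** Phase Ib patients at the MTD belong to a dose that was kept because few of them had a cycle-1 DLT. The plan does not say whether they form the first 6 and first 12, or how many carry over; Section 6.2 requires measurable disease only in phase IIa. Reading Sections 9.5 and 14.0 together, their DLTs are most naturally counted over cycles 1-4, under the Section 9.3.2 definition without the criterion it reserves for phase Ib. No sentence says so for carried-over patients.

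This is the only numerical stopping rule for the phase IIa safety endpoint; the committee oversight in Section 16.2 is additional. Most of the tabled stopping probability comes from the first look, which is the look that screened patients would fill.

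**Working it through.** **1. The table.** Let *p* be the true DLT rate and *c* the final cut. With independent binomial increments of 6, 6 and 8 patients,

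S = P(X₆ ≥ 3) + P(X₆ ≤ 2, X₁₂ ≥ 6) + P(X₆ ≤ 2, X₁₂ ≤ 5, X₂₀ ≥ c).

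At *p* = 0.40 the first term is 1 − (0.0467 + 0.1866 + 0.3110) = 0.456 and the second is 0.064. The third is 0.029 for c = 10 and 0.007 for c = 11. By exact recursion:

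| True rate | 5% | 10% | 15% | 20% | 25% | 30% | 35% | 40% | 50% |
|---|---|---|---|---|---|---|---|---|---|
| Printed | 0.002 | 0.016 | 0.049 | 0.104 | 0.184 | 0.289 | 0.413 | 0.548 | 0.797 |
| c = 10 | 0.002 | 0.016 | 0.049 | 0.104 | 0.184 | 0.289 | 0.413 | 0.548 | 0.797 |
| c = 11 (text) | 0.002 | 0.016 | 0.049 | 0.104 | 0.183 | 0.283 | 0.400 | 0.526 | 0.765 |

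Of the 6 × 12 × 20 = 1,440 possible sets of cuts at 6, 12 and 20 patients, only 3/6/10 fits the printed row within 0.001. The match also shows that the table treats all 20 patients as independent with one common rate. The first look alone gives 0.256 / 0.456 / 0.656 at 30/40/50%.

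**2. Screened patients in the first look.** Inputs: six patients at the MTD (Section 14.0) with at most 1 cycle-1 DLT. That limit is inferred, because Section 14.0 states no acceptance limit for the three confirmatory patients. Let *q* be the cycle-1 risk, an assumption because the documents give no split by cycle. The risk in cycles 2-4 for a patient without a cycle-1 DLT is then (p − q)/(1 − q).

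Worked case, *p* = 0.40 with half the risk in cycle 1:

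- q = 0.20 and the later risk is 0.20/0.80 = 0.25.
- P(at most 1 of 6 in cycle 1) = 0.8⁶ + 6 × 0.2 × 0.8⁵ = 0.262 + 0.393 = 0.655. Given this, the chances of 0 and 1 early DLTs are 0.4 and 0.6.
- P(first look met) = 0.4 × P(Bin(6, 0.25) ≥ 3) + 0.6 × P(Bin(5, 0.25) ≥ 2) = 0.4 × 0.169 + 0.6 × 0.367 = 0.288, against 0.456 for unselected patients.
- Adding the later looks (0.076 and 0.036) gives 0.400, against 0.548.

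Phase IIa stopping probability at 30/40/50%:

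| Scenario | Equal hazard per cycle, q = 1 − (1 − p)^0.25 | Half in cycle 1, q = p/2 | All in cycle 1, q = p |
|---|---|---|---|
| Six carried over, c = 10 | 0.248 / 0.490 / 0.747 | 0.179 / 0.400 / 0.675 | 0.013 / 0.069 / 0.226 |
| Six carried over, c = 11 | 0.242 / 0.466 / 0.707 | 0.173 / 0.373 / 0.625 | 0.009 / 0.042 / 0.139 |
| Three carried over, c = 10 | 0.270 / 0.520 / 0.772 | 0.238 / 0.478 / 0.740 | 0.126 / 0.294 / 0.544 |

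The three-patient row treats measurable disease as independent of DLT. With no acceptance limit for the confirmatory patients, the six-patient figures at 40% (c = 10) are 0.501, 0.428 and 0.146.

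**3. New patients only at 6 and 12.** With the six phase Ib patients entering at the final count (c = 10), the ranges over the three risk splits are 0.282-0.287 / 0.519-0.540 / 0.747-0.786, close to the table.

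**4. Screen and rule together.** P(dose rejected by either) = 1 − P(at most 1 of 6) × (1 − S). In the worked case this is 1 − 0.655 × 0.600 = 0.607. Over the three splits, with six counted first:

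- c = 10: 0.313-0.585 / 0.569-0.783 / 0.809-0.915, above the table throughout.
- c = 11: 0.307-0.584 / 0.549-0.776 / 0.779-0.906, below the table only at 50% with equal hazard (0.779 against 0.797).

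**5. Pooled DLT rate.** In the worked case the six are expected to have 0.4 × 6 × 0.25 + 0.6 × (1 + 5 × 0.25) = 1.95 DLTs, against 6 × 0.40 = 2.4. The pooled rate is therefore low by (2.4 − 1.95)/20, about 2.3 points. Over the splits (equal, half, all) the shortfall is 0.6, 1.6 or 5.4 points at 30% and 0.9, 2.3 or 8.0 points at 40%, ignoring early stopping.

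**The case against.** The final-cut mismatch is small. Text and table agree to three decimals up to a 20% rate, differ by 0.006 at 30% and by at most 0.032 at 50%. The cut applies only at the 20th patient, when accrual is complete. The looks at 6 and 12 agree in text and table. All of this stands, but the two cuts still give opposite decisions at 10 of 20.

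On selection, a stopping probability at a fixed true rate is an ordinary operating characteristic and does not claim to be conditional on having passed a 3+3 screen. The lowest figures need six carried over, all placed first, and all risk in cycle 1; a dose with a 40% rate would then pass the screen only 23% of the time, and one with 50% only 11%. Whole-trial protection is not shown to be lost. These points stand, and they limit the claim to the stated phase IIa figures and the undefined first look. They do not remove it: the table is offered as the probability for this rule, whose 20 patients include screened ones, and a reader cannot tell who fills the first look.

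It can also be said that the phase Ib DLT count is already known, so conditioning on a generic limit is artificial. That bears on how the table is recomputed, not on whether it needs restating.

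**Conclusion.** The concern holds. The mismatch between text and table at the final cut is certain and rests on no assumption; it is worth at most 3.2 points, at a 50% DLT rate. The documents do not show which cut was intended.

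The population point holds conditionally. If screened phase Ib patients fill the first look, the table overstates phase IIa stopping: at 40%, by about 6 points with equal hazard (0.548 − 0.490), about 15 with half the risk in cycle 1 (0.548 − 0.400), and far more in the extreme case. If the early looks use new patients only, the table is nearly right. The size depends on the number carried over, their place in the sequence, the cycle-1 share of risk and the inferred limit of 1 in 6, none of which the documents settle. Patients replaced for low drug exposure and the DLT criterion reserved for phase Ib were not modelled. This should be clarified; it does not show that the trial as a whole is less safe than stated.

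**What to change.** 1. Make the final cut the same in the text and the table of Section 14.0.
2. State whether phase Ib MTD patients enter the looks at 6 and 12, and how many are counted; the MTD is already fixed, so the number can be given. State that their DLTs are counted over cycles 1-4 under the Section 9.3.2 definition without the criterion reserved for phase Ib.
3. Recompute the table for that rule, conditional on the 3+3 screen if these patients are counted first.
4. Report the DLT rate in newly enrolled patients beside the pooled rate.

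The boundaries at 6 and 12 need not change. The cost is a text amendment to Section 14.0, one sentence in Section 9.3 or 9.5, and a new table, with IRB approval at each site (Section 16.3.1). No extra patients or procedures are needed. The stated stopping probabilities may look slightly less favourable.
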